8.2 Trial Design

This is a Phase II prospective, multi-center, single-blind, randomized clinical trial evaluating safety and tolerability in adult recipients of an allo-HSCT with BOS. Twenty-four patients are planned for enrollment. The clinical trial will be conducted in up to 20 centers in Europe. Patients will be randomly allocated 1:1:1 to receive either L-CsA (10 mg bid or 5 mg bid) plus SoC or 0 mg L-CsA (placebo) plus SoC. IMP will be administered for up to 12 weeks.

8.3 Stratification and Randomization

At the baseline visit (see [Section 13.2.2](#)), after all inclusion and exclusion criteria have been fully evaluated, eligible patients will be assigned to one of the three treatment groups at a ratio of 1:1:1 by means of block randomization. Randomization will be performed by a statistician otherwise not involved with the trial, using validated random number generator software. The randomization code of each patient will be provided to the Investigator after compliance with all eligibility criteria has been confirmed, through the electronic Case Report Form (eCRF) into which the generated random code list will be uploaded. Each patient will be assigned a number as part of the randomization process. The number assigned to a patient will become that patient's unique treatment number throughout the clinical trial and cannot be re-assigned to another patient.

No stratification will be performed.

8.3.1 Blinding

This is a single-blind trial. Due to the different appearance of the three tested strengths of IMP, a full blinding of the study was not possible. Only the randomized study patients will be blinded to study treatment assignment. For details of the blinding of the Data Monitoring Committee members, see [Section 12.2](#).

8.3.2 Investigational Medicinal Product: Treatment, Dosage and Administration

8.3.2.1 Formulation of L-CsA

The composition of the L-CsA formulation is shown in [Table 1](#). It is a lyophilisate intended for reconstitution with 0.25% NaCl. The formulation is developed for inhalation use and adjusted to physiological tolerable values of pH (6.5 ± 0.3) and osmolality 430-550 mOsmol/kg).

Table 1: Qualitative Composition of the IMP

Ingredient	Function	Quality
Cyclosporine A	Active ingredient	Ph Eur ¹
Lipoid S100	Carrier	non compendial
Polysorbate 80	Surfactant	Ph Eur
Disodium hydrogen phosphate dodecahydrate	Buffer	Ph Eur
Sodium dihydrogen phosphate dihydrate	Buffer	Ph Eur
Disodium edetate dihydrate	Stabilizer	Ph Eur
Sucrose	Lyoprotectant	Ph Eur
Water	Dispersion medium	Ph Eur/USP ²

1: European Pharmacopeia

2: United States Pharmacopeia

The particle size of the liposomes is in the range of 40-100 nm with a PI of not more than 0.50, which indicates the width of the size distribution. Values of polydispersity index above 0.5 indicate a broad distribution. For colloidal disperse systems a PI of 0.20 to 0.50 is appropriate.

The IMP (L-CsA) and 0.25% NaCl for reconstitution will be supplied by the IMP depot on behalf of the sponsor:

PPD

Germany

8.3.2.2 Treatment and Dosage

After Screening, patients complying with all inclusion and exclusion criteria (see [Sections 9.1](#) and [9.2](#)) will be randomized to one of the following treatments:

Treatment A (L-CsA 10 mg treatment plus SoC):

L-CsA 10 mg/2.5 mL bid for a maximum of 12 weeks
plus
SoC therapy

Treatment B (L-CsA 5 mg treatment plus SoC):

L-CsA 5 mg/1.25 mL bid for a maximum of 12 weeks
plus
SoC therapy

Treatment C (L-CsA 0 mg (Placebo) plus SoC):

L-CsA 0 mg/2.5 mL bid for a maximum of 12 weeks
plus
SoC therapy

8.3.2.3 Administration of IMP

In clinical trials 12011.201 and clinical trial AI 001 totaling > 1100 patient months of exposure, L-CsA was well tolerated. Patients will be educated regarding use of the L-CsA **CCI** and administration of the first dose will be observed. At subsequent study visits, it will be requested that the patient self-administer a dose of IMP while observed by study personnel.

Each patient will receive two IMP administrations per day, one in the morning and one in the evening. The inhalations are scheduled to be taken approximately 12 hours (but not less than 6 hours) apart, e.g., at 8:00 a.m. and 8:00 p.m. each day. Instructions for administration should be followed as described in the Instructions For Use.

Handling of IMP Inhalation:

Each patient will open a glass vial by lifting up the plastic disk/cap, lifting up the metal flap to remove the metal ring, metal cap, and the rubber stopper. The plastic ampoule containing 1.2 ml or 2.4 mL of the 0.25% NaCl as solvent will be opened by twisting the head part several times in one direction. The NaCl solution will be squeezed into the glass vial containing the whitish lyophilisate cake. The glass vial will be re-closed with the rubber stopper and swirled gently without spilling any liquid for a minimum of 1 minute and up to 5 minutes, until the visible particles are completely dissolved. Shaking of the vial must be avoided to prevent foaming of the reconstituted solution.

Next, the reconstituted IMP should be poured into the L-CsA **CCI** chamber. The nebulizer should be kept horizontal during operation. During inhalation, the patient should sit in an upright position and inhale and exhale deeply through the mouthpiece of the nebulizer without interruption until nebulization shuts off automatically. The solution is for single use only, and no remaining solution should be left in the glass vial. All other clinical trial materials, including unused IMP, must be brought back to the clinical trial center at each scheduled visit for drug and device accountability. After completion of the inhalation, the patient should remove all excess IMP in the mouth and pharynx by rinsing and gargling with water and subsequently discharging the solution.

Interruption of IMP Inhalation:

If a patient needs to temporarily interrupt IMP inhalation (e.g., due to coughing), the patient should turn off the device and turn it back on when ready to resume inhalation.

IMP maybe temporarily discontinued as deemed necessary by the investigator (see [Section 9.3.1](#)) and will be documented in the eCRF.

8.4 Investigational Medicinal Product Packaging, Labeling and Storage

8.4.1 Packaging and Labeling of IMP

Packaging

The IMP will be provided as 0 mg and 10 mg L-CsA lyophilisate in glass vials type I with grey rubber stoppers and an aluminum cap with a yellow plastic disk and stored in an outer packaging box consisting of 60 vials with the L-CsA/placebo and 70 plastic ampoules containing 2.4 mL 0.25% NaCl for reconstitution. The 5 mg L-CsA lyophilisate will be supplied in glass vials type I with grey rubber stoppers and an aluminum cap with a green plastic disk and stored in an outer packaging box consisting of 60 vials with the L-CsA and 70 plastic ampoules containing 1.2 mL 0.25% NaCl for reconstitution.

The IMP will be labelled in compliance with Good Manufacturing Practice (GMP) specifications according to applicable regulations.

8.4.2 Storage

The unopened IMP must be kept in a secure, locked, temperature-controlled location with access to authorized staff only. IMP should be stored not above 25 °C protected from light.

8.4.3 Inhalation Device Packaging

The Investigational **CCI** Nebulizer System consists of the following two packages:

1) Controller Kit

The controller kit will be provided at randomization visit and includes

- 1x eTrack Controller
- 1x Nebulizer Handset including connection cord, an AC power supply and 4 “AA” batteries
- 1x Easycare cleaning aid
- 1x Carrying bag
- 1x Instructions For Use
- 2x Aerosol Heads

2) **CCI** in combination with L-CsA Kit below

Monthly Supply –At Each following Clinic Visit

8.5 Stopping Rules and Discontinuation Criteria

8.5.1 Patient Level

Regular termination of clinical trial participation:

The investigational treatment will be terminated after 12 weeks (End of Treatment [EoT]). The treatment period will be followed by a 2-week follow-up period (End of Study [EoS]). Any patients with ongoing AEs and SAEs will be followed-up until recovery or stabilization of the AE/SAE.

Premature termination of clinical trial participation:

- Patients may discontinue participation in the clinical trial at any time by revoking their informed consent.
- The Investigator may withdraw a patient at any time if it is in the best interest of the patient based upon clinical assessments.
- Patient is lost to follow-up
- Pregnancy (the patient will be followed via the sponsor's safety department)
- Termination of the clinical trial as a whole by Zambon SpA as defined in [section 8.5.3](#).

If the participant fails to return for clinical follow-up, the patient will be contacted by telephone or a letter will be sent requesting a clinic visit (EoS), and the reason for non-compliance will be documented. The final visit will encompass the assessments listed under EoS Visit (Visit 6; [Section 13.2.5](#)). Additionally, used and unused IMP and inhalation device will be retrieved, if applicable. Zambon SpA will be notified that the patient has terminated clinical trial participation.

8.5.2 Center Level

Regular termination of clinical trial centers:

All centers will be closed after patients have completed clinical trial participation and the database has been locked.

Premature termination of a clinical trial center:

The sponsor may close a center for the following reasons:

- In case of repeated and continuous violations of GCP and applicable regulations
- Inaccurate or incomplete data collection
- Falsification of records
- Failure to adhere to the protocol
- Organizational or structural changes in the center which challenge the requirements or qualification for clinical trial participation (e.g., change of investigator, shift of center activities)

In case a center is closed for any of the reasons above, efforts will be made to ensure the safety and data reliability of ongoing patients until clinical trial completion.

8.5.3 Clinical Trial Level

Regular termination of the clinical trial:

The clinical trial will be considered complete after the pre-defined number of patients have been randomized and completed their clinical trial participation. The last visit of the last patient is the defined end of the study.

Premature termination of the clinical trial:

- Serious safety concerns that indicate a potential health hazard caused by treatment with the IMP (termination due to safety issues)
- The clinical trial may be discontinued at any time for reasons such as but not limited to medical futility and administrative reasons, upon the discretion of Zambon SpA.

In this case, an abbreviated clinical study report will be reported to Competent Authorities and Ethics Committees according to applicable regulatory requirements. The Investigator must notify his/her EC of clinical trial closure.

8.6 Investigational Medicinal Product: Supply and Accountability

Each Investigator is responsible for ensuring that deliveries of IMP vials and boxes, L-CsA CCI and other clinical trial materials are correctly received and recorded, that these are handled and stored safely in a locked and temperature controlled storage place with access for authorised study staff only and that they are used in accordance with this protocol. In addition, the Investigator will monitor each patient's treatment compliance by counting the used/unused drug vials at each visit.

For the purpose of this trial patients will be regarded as compliant if no more than 45 vials of IMP over the entire treatment period of 12 weeks are returned as unused – this corresponds to approximately 75% treatment compliance. The reason for non-compliance shall be documented according on the respective eCRF.

Unused IMP vials, ampoules, boxes, and L-CsA CCI must be returned or destroyed on-site after accountability has been completed and destruction is approved by Zambon SpA. A list of IMP, L-CsA CCI, and other materials received, used, returned, or destroyed must be prepared, completed and signed by the Investigator; any discrepancies must be accounted for.

COVID-19 specific consideration: the patients will be supplied during V1 with the full amount of study medication needed, to cover the total treatment period of 12 weeks. Patient has to bring all study medication back to the site at EoT Visit V5 for Drug Accountability.

9 SELECTION AND WITHDRAWAL OF PATIENTS

9.1 Patient Inclusion Criteria

1. Age \geq 18 years
2. Patients must have undergone hematopoietic stem cell transplantation and have documented diagnosis of chronic Graft versus Host Disease (cGvHD) guided by the NIH consensus criteria.
3. Patients must have been diagnosed with BOS within >6 months and ≤ 3 years at Screening visit.
4. Spirometry test carried out at Screening visit must show:
A FEV₁ above 51% of predicted
AND
A $\geq 10\%$ decline in FEV₁ (L) within 2 years
5. Patient must be capable of understanding the purposes and risks of the study, has given written informed consent, and agrees to comply with the study requirements.
6. Women of childbearing potential must have a negative serum or urine pregnancy test within 7 days prior to randomization and must agree to use one of the methods of contraception listed in [Appendix II](#) through their End of Study Visit.

9.2 Patient Exclusion Criteria

1. Other acute or chronic restrictive or obstructive lung diseases, including but not limited to: Patients with clinically active asthma (variable and recurring symptoms of airflow obstruction and bronchial hyper-responsiveness), chronic obstructive pulmonary disease, interstitial lung disease, or cryptogenic organizing pneumonia or other causes of restrictive lung disease such as neuromuscular weakness or diaphragmatic paralysis.
2. Any acute pulmonary bacterial, viral (as confirmed by multiplex PCR) or fungal infection not successfully resolved at least 4 weeks prior to the Screening Visit.
3. Chronic renal dysfunction with serum creatinine ≥ 2.5 mg/dL.
4. Chronic hepatic dysfunction with serum total bilirubin > 5 x upper limit of normal (ULN), transaminases > 5 x ULN, or alkaline phosphatase > 5 x ULN.
5. Evidence of clinical relapse of the primary malignancy, according to investigator's judgement, which warranted allogeneic bone marrow transplant.
6. Use of azithromycin within 4 weeks prior to Randomization (Visit 1).
7. Chronic oxygen use or use of non-invasive ventilation.
8. Active smokers (i.e. any kind of inhaled nicotine consumption).
9. Pregnant women or women who are unwilling to use appropriate birth control to avoid pregnancy over the course of the clinical trial (for details see [Appendix II](#)).
10. Women who are currently breastfeeding.
11. Known hypersensitivity to L-CsA or to cyclosporine A.
12. Patients with life-expectancy of less than 6 months.
13. Receipt of an investigational drug as part of a clinical trial within 4 weeks prior to the Screening Visit. Participation in registries, , is allowed

14. Psychiatric disorders or altered mental status precluding understanding of the informed consent process and/or completion of the necessary procedures.
15. Any co-existing medical condition that in the Investigator's judgment will substantially increase the risk associated with the patient's participation in the clinical trial.
16. Pre-scheduled hospitalizations, surgeries or interventions planned to be performed after obtaining Informed Consent for this study.

9.3 Patient Withdrawal Criteria

In the event of patient withdrawal, the Investigator must complete the appropriate end of study form in the eCRF as soon as possible after withdrawal, stating the reason and date of withdrawal. An automated e-mail alert will be generated by the eCRF system and will be sent to the Clinical Research Organization (CRO).

9.3.1 Procedures of Patient Withdrawal and IMP discontinuation

Withdrawal:

The patient is free to withdraw from the clinical trial for any reason and at any time without giving a reason for doing so and without penalty or prejudice. The Investigator is also free to terminate a patient's involvement in the clinical trial at any time if the patient's clinical condition warrants it. In case of early withdrawal, the patient will be encouraged to perform a final visit. The final visit will encompass the assessments listed under EoS Visit ([Section 13.2.5](#)).

Additionally, used and unused IMP and inhalation device will be retrieved, if applicable. Zambon SpA will be notified by the Investigator via entry in and notification by the eCRF that the patient has terminated clinical trial participation.

IMP discontinuation

The Investigator or patient is free to discontinue regular intake of IMP, if the clinical condition of the patient or other serious reasons warrant it. Reasons for discontinuation of IMP may include (but are not limited to) the following:

- Significant respiratory infection requiring therapy
- Respiratory failure from any cause
- Mechanical ventilation

If 10 or more consecutive doses of IMP are missed, regardless of reason, then IMP will be considered as discontinued and should not be resumed. If IMP inhalation is discontinued, the patient will be asked to return for clinical trial visits according to the visit schedule defined in the protocol but shall not receive IMP.

Stopping criteria are outlined in detail in [Section 8.5.1](#).

9.3.2 Type and Timing of Data Collection for Patient Withdrawal and IMP discontinuation

All cases of patient withdrawal or discontinuation of IMP will be recorded on the applicable eCRF pages by the Investigator including date and reason.

Patients who are discontinued should have the final clinical trial visit procedures performed within 1 month after stopping IMP, if possible. For details of the procedures, please refer to [Section 13.2.5, Visit 6/End of Study](#).

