9.3.3 Replacement of Withdrawn Patients

Patients withdrawn before randomization will be regarded as screen failures. A sufficient number of patients will be screened until the pre-defined number of randomized patients has been reached. Randomized patients will not be replaced. However, patients prematurely withdrawn from treatment should be encouraged to continue to participate in the clinical trial until the scheduled end. The eligibility of prematurely withdrawn patients for the different analysis populations will be determined in a blind data review meeting with consideration of the definition of these analysis populations provided in [Section 14.1](#).

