9.3.4 Follow-up of Withdrawn Patients

All patients withdrawn from IMP should be followed for AEs and SAEs for a further 4 weeks from the time of withdrawal. In case of patient consent withdrawal, the patient will be encouraged to complete an EoS Visit ([Section 13.2.5](#)).

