13 VISIT SCHEDULE

All clinical trial visits, investigations and activities are listed in the Clinical Trial Schedule of Activities below. Further details on the methodology of these investigations and activities are described in detail in [Section 11](#) and [Section 12](#). The investigator will adhere to the visit and procedure schedule as closely as possible.

All patients assigned to a randomization number will be followed according to the protocol unless consent for follow-up is withdrawn. The Sponsor must be notified of all deviations from the protocol visit schedule or evaluations, and these visits/evaluations, if applicable, must be rescheduled or performed at the closest possible time to the original schedule.

Proper patient understanding and competency of the L-CsA **CCI** use will be ensured in an individual training by the responsible clinic personnel. The patient will be administering the drug independently under supervision to verify patient competency with the equipment and drug tolerability.

For emergency and other unscheduled visits to a medical facility other than the clinical trial site, medical records of the visit should be obtained by the Investigator.

If a patient prematurely discontinues clinical trial participation for any reason, e.g., the patient withdraws consent for further participation in the clinical trial, the evaluation listed under “End of Study Visit (EoS)” (Visit 6) should be completed prior to discontinuation whenever possible (the reason for premature withdrawal should always be documented).

Schedule of Activities

Clinical Trial Period	Screening	Treatment						Follow-Up
Visit Number	-	V 1	V 2	V 3	V 4	V 5 / EOT	Remote Visits	V 6 / EoS
Week & Window	W -4 to W 0	W 0 Day 1	W 2 ± 3 Days	W 4 ± 3 Days	W 8 ± 7 Days	W 12 ± 7 Days	V3, V4 and V6 can be performed remotely	W 14 ± 3 Days
Informed Consent ¹	X							
Demographics/Medical History	X	-						
Inclusion/Exclusion criteria	X							
Serum/Urine Pregnancy Test	X	X	X	X	X	X		X
Physical Examination ²	X	X	X	X	X	X		X
Vital signs ³	X	X	X	X	X	X		X
Clinical Laboratory Tests ⁴	X	X	X	X	X	X		X
PK Blood Sampling ⁵		X	X	X	X	X		
Spirometry ⁷	X	X ⁶	X ⁶	X ⁶	X ⁶	X ⁶		
Randomization		X						
SF-36		X	X	X	X	X	X ⁸	
CGI Questionnaire		X	X	X	X	X		
Investigator's Tolerability Assessment				X		X		
Local IMP Tolerability		X	X	X	X	X		
IMP Administration				Twice daily administration			X	
Concomitant Medication	X	X	X	X	X	X	X	X

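### Protocol 9.3.2 can be read as sending patients who stop only IMP to a final EoS-type visit within a month, while 9.3.1, 9.3.3 and 13 keep them on the visit schedule, so later visit-based outcomes of these patients may go uncollected

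*Protocol*

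**What the plan says.** Five places in the protocol deal with what happens after a patient stops IMP.

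- **9.3.1** has two headed paths. Under withdrawal from the trial, the patient is encouraged to have a final visit on the EoS list. Under IMP discontinuation: "If IMP inhalation is discontinued, the patient will be asked to return for clinical trial visits according to the visit schedule defined in the protocol", without receiving IMP.
- **9.3.2** is titled for both groups. It opens with "All cases of patient withdrawal or discontinuation of IMP will be recorded on the applicable eCRF pages" and continues with "Patients who are discontinued should have the final clinical trial visit procedures performed within 1 month after stopping IMP, if possible". For the procedures it refers to 13.2.5 (Visit 6/EoS).
- **9.3.3** says that "patients prematurely withdrawn from treatment should be encouraged to continue to participate in the clinical trial until the scheduled end".
- **9.3.4** sets a further period: "All patients withdrawn from IMP should be followed for AEs and SAEs for a further 4 weeks from the time of withdrawal".
- **13** says "All patients assigned to a randomization number will be followed according to the protocol unless consent for follow-up is withdrawn". It ties the early EoS evaluation to leaving the trial: "If a patient prematurely discontinues clinical trial participation for any reason".

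The EoS list in 13.2.5 consists of physical examination, vital signs, laboratory tests, pregnancy test, concomitant medication and AEs.

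The SAP does not say which path applies. SAP 9.1.1 rules out imputation for efficacy. SAP 15.1 and 15.2 fit an MMRM to all available data from Weeks 2 to 12. SAP 13.2 compares the CGI between groups at Visit 3 and Visit 5/EoT, and tabulates the investigator's tolerability assessment at Visit 3. SAP 13 allows for an EoT visit held on or before Visit 3.

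**The concern.** In 9.3.2 the clock runs from stopping IMP, the section title names IMP discontinuation, and nothing limits the sentence to patients who leave the trial. A site that opens 9.3.2 for a patient who has stopped only IMP can reasonably book an EoS visit and close the case. A site that opens 9.3.1 will bring the same patient back until Week 14.

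Patients who stop IMP carry much of the information in a trial whose primary and secondary assessments are tolerability and safety at 4 and 12 weeks. If their later visits are missing, the loss is selective: the remaining by-visit data come more from patients who stayed on IMP. The EoS visit cannot stand in for Visits 3, 4 or 5, because it omits the outcomes analysed at those visits. The SAP foresees an early EoT visit, which would include those outcomes, but no protocol passage sends a patient who stops IMP to one. Protocol 9.3.2 points to EoS.

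**Working it through.** The plan gives no figure to reproduce: the sample size of 24 rests on feasibility, and no stopping or dropout rate is stated. The check is a comparison of texts, then schedule arithmetic.

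**1. Can the passages be reconciled as written?** If 9.3.2 applies only to patients who leave the trial, it agrees with 9.3.1, 9.3.3 and 13. If it applies to patients who stop only IMP, and the visit is final in the ordinary sense, it does not. The text allows either reading. Protocol 9.3.1 heads trial exit as withdrawal and uses discontinuation for IMP, while 8.5.1 and 13 also speak of discontinuing participation. The vocabulary therefore does not settle it.

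**2. Which visits are at risk if a site treats the visit as final?** Inputs from the schedule in Protocol 13, in days from Visit 1 (week × 7):

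- Visit 3: day 28 ± 3, window 25 to 31
- Visit 4: day 56 ± 7, window 49 to 63
- Visit 5: day 84 ± 7, window 77 to 91

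Assumption: 1 month = 30 days. A patient who stops on day *s* has the final visit by day *s* + 30 at the latest. A scheduled visit can still be held if its window opens by then.

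- Visit 4 is reachable if *s* + 30 ≥ 49, so *s* ≥ 19 (19/7 = 2.7 weeks).
- Visit 5 is reachable if *s* + 30 ≥ 77, so *s* ≥ 47 (47/7 = 6.7 weeks).
- Visit 3 is always reachable, because the latest final visit always falls after its window opens on day 25.

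| Stop day | Latest final visit | Out of reach with latest final visit | Lost if final visit is held at once |
|---|---|---|---|
| 7 | 37 | Weeks 8, 12 | Weeks 2, 4, 8, 12 |
| 14 | 44 | Weeks 8, 12 | Weeks 4, 8, 12 |
| 21 | 51 | Week 12 | Weeks 4, 8, 12 |
| 28 | 58 | Week 12 | Weeks 8, 12 |
| 42 | 72 | Week 12 | Weeks 8, 12 |
| 47 | 77 | none | Weeks 8, 12 |

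(For the day 14 and day 28 rows, the visit due that day is taken as held.) On nominal visit days, without windows, a day 21 stop would also miss Week 8, since 51 < 56. The windows make that loss avoidable.

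**3. Does 9.3.4 settle it?** Four weeks of AE/SAE follow-up from a stop before Week 10 ends before Week 14 (10 + 4 = 14). Read alone, it also suggests an end of follow-up earlier than the schedule in 13.

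**4. Precision.** One stopper is 1/8 = 12.5% of an arm. If *d* of 8 are missing at a visit, the standard error of that arm's observed mean is multiplied by √(8/(8 − *d*)) at equal SD:

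- *d* = 1: √(8/7) = 1.07, up 7%
- *d* = 2: √(8/6) = 1.15, up 15%
- *d* = 3: √(8/5) = 1.26, up 26%

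For the difference between two arms when only one loses patients, the factor is √[(1/(8 − *d*) + 1/8)/(2/8)] = 1.04, 1.08 and 1.14. These factors are for observed means. An MMRM recovers part of the loss from earlier visits.

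**The case against.** The best defence is that 9.3.2 concerns patients who leave the trial. It points to the same EoS list that 9.3.1 uses for withdrawal, and 8.5.1 and 13 tie the early EoS visit to ending participation. Patients who stop only IMP already have an explicit rule in 9.3.1. A patient who leaves the trial also stops IMP, so counting from that date is not odd. This reading is plausible and probably intended, but 9.3.2 does not state it.

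Several stronger conclusions are tempting, and the documents do not support them:

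- *That the two instructions cannot both be followed.* Protocol 9.3.2 is soft and cancels no visit. Every item on the EoS list is also on the Visit 2 to 5 list, so an on-site scheduled visit within the month would satisfy both. The conflict arises only if the visit is treated as the end of the schedule.
- *That a Week 3 stopper must lose Visits 4 and 5.* The Visit 4 window opens on day 49 and the month ends on day 51.
- *That the primary 4-week data are lost.* SAP 13.1 counts a local tolerability event only if it appears within 1 hour after an inhalation, so a patient off IMP cannot add one. AEs and SAEs are followed for 4 weeks after withdrawal from IMP. Laboratory tests, vital signs and examination are on the EoS list. What remains exposed at Week 4 is the CGI, the investigator's rating, spirometry, SF-36 and the trough sample, and only if the final visit precedes Visit 3.
- *That most centres contribute one or two patients, so site reading decides who is observed.* The figure of 20 centres is an upper limit, and no enrolment per centre is given.

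It also stands that the trial is purely descriptive and that spirometry and SF-36 are exploratory. The MMRM uses stoppers' earlier values, so missing later visits do not by themselves bias it. That protection does not reach the CGI and the investigator's rating, which are compared by rank tests on the patients observed.

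**Conclusion.** The point holds as an ambiguity in data collection after IMP is stopped, not as an outright contradiction. A site could reasonably end visits about a month after the stop, and the outcomes then lost would come only from stoppers. With the final visit as late as allowed, Week 12 is out of reach for stops before about Week 7, and Week 8 for stops in roughly the first 3 weeks. An earlier final visit widens the loss. Week 4 visit-based outcomes are lost only if the final visit comes before Visit 3. AE capture and post-inhalation events in the first 4 weeks are little affected.

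This rests on a 30-day month, on the visit windows in Protocol 13, and on a site treating the visit as the end of participation. The loss of precision, about 7% to 26% on the standard error of one arm's observed mean, assumes 1 to 3 stoppers among 8 patients and equal SD. The documents give no rate. The direction and size of any bias cannot be computed from them. The wording should be corrected, because the remedy is simple and the patients concerned matter most for tolerability.

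**What to change.** Reconcile Protocol 9.3.1, 9.3.2, 9.3.3, 9.3.4 and 13 on visits after IMP is stopped:

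1. Limit the final-visit sentence in 9.3.2 to patients who end trial participation.
2. State there that patients who stop only IMP attend the remaining scheduled visits under 9.3.1, with all assessments of those visits, IMP administration aside.
3. State in 9.3.4 that the 4-week AE/SAE follow-up is a minimum and does not shorten that schedule.
4. Add a sentence to the SAP on how data collected after IMP is stopped enter the by-visit and MMRM analyses.

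The cost is a short protocol clarification, a letter to sites and a line in the SAP. It adds no visits beyond those 9.3.1 already requests and changes no rule on when IMP is stopped.
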